| Individual FU duration | 
Maximum 14 months for each patient
 
The follow up period starts from the date of the first Phased RFA procedure (hereafter „index“) and lasts 12 (+ 2) months.
 
In case the index procedure is unsuccessful (e.g. not all PVIs reached/isolated, procedure prematurely terminated due to patient's clinical status or technical issues), patients will continue their participation in the registry until the end of defined FU period.
 | | | | | | | | |
| Time schedule (tentative) for calendar years | 
 
 Preparation	Q2-Q4 2014	
 
 Recruitment	Q1 2015 – Q2 2018	
 
 Intended last patient out	Q3 2019	
 
 Final Report	Q1 2020	
 
 | Preparation | Q2-Q4 2014 | Recruitment | Q1 2015 – Q2 2018 | Intended last patient out | Q3 2019 | Final Report | Q1 2020 |
| Preparation | Q2-Q4 2014 | | | | | | | | |
| Recruitment | Q1 2015 – Q2 2018 | | | | | | | | |
| Intended last patient out | Q3 2019 | | | | | | | | |
| Final Report | Q1 2020 | | | | | | | | |

1 Introduction

AF is the most common of the sustained arrhythmias affecting millions of people worldwide, with an estimated 2.2 million people in the United States (US) and 4.5 million in the European Union (EU) afflicted with the disorder (1). The overall prevalence of AF is between 2.3% and 2.8% (2). However, the prevalence increases with advancing age, with approximately 10% prevalence of AF in persons aged 70 years or older. The causes of AF are numerous and varied, including ischemic heart disease, post-cardiac surgery, sick sinus syndrome, hypertensive heart disease, idiopathic causes, etc. (3). The prognosis is related to the underlying cause of the disease, with idiopathic causes having the best prognosis and ischemic cardiomyopathy having a poor prognosis (4). AF is associated with an increased incidence of thromboembolic events (stroke and transient ischemia attack), heart failure, and all-cause mortality (5). It is a debilitating disease with symptoms that reduce quality of life and increase the number of hospitalizations. The management of AF is a challenge due to a heterogeneous etiology and tendency for self-propagation of AF, "AF begets AF".

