3.4 Methodology

Patient can sign PIC/PDRF 14 days prior to the scheduled Phased RFA procedure to have sufficient time to consider the participation in the registry.

Observations will be documented at baseline, ablation procedure/hospital discharge and whenever patients visit the medical center with regard to AF recurrence, catheter ablations, Adverse Events, regular medical checkup etc.

Patient will be followed up for minimum 12 and maximum 14 months following first (hereafter "index") Phased RFA procedure. In case the index procedure is performed, but is not successful for medical or technical reasons, patients will stay in the registry until the end of the FU period.

Figure 3-5 provides an overview of the data entry flow chart. The process of data collection is described in Chapter 7. Furthermore, an overview of data to be collected is provided in Table 7-1.

At the baseline visit demographics, medical history, diagnostics, cardiovascular medication and quality of life (QoL) questionnaire ("AFEQT") will be recorded. During the index Phased RFA and all re-do Phased RFA procedures, related variables will be collected including: anticoagulation therapy, general procedure summary, consumables, PV isolation confirmation, adverse events (AE) assessment and hospital discharge status. During the FU period, information about in-hospital visits will be captured in the "General FU" CRFs. The "General FU" CRF contains data about arrhythmia diagnostics, symptoms, hospitalization and cardioversions (from previous visit date to actual visit), re -ablation information, cardiovascular medication, and AE assessment.

At 12 months FU, patients will be either followed up in the medical center ("12 months FU") or by phone ("12 months FU by phone"). Data recorded on the "12 month follow up" CRF is equivalent to the "General FU" CRF, with the addition of the QoL questionnaire (AFEQT). If patient has no reason to visit the medical center between 12 and 13 month after the index procedure, he might be called by study personnel and asked questions for about 15-20 min about any AF symptoms, hospitalizations, AF cardioversions since the previous visit, current medications and quality of life. Whenever 12 months FU performed by phone, data received via CareLink may be used for confirmation of rhythm disturbances. The interview does not replace a medical checkup for the patient and serves as data collection only.

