4.4.2 Statistical methods for additional objective

Estimate Phased RFA procedure safety

Rational: Phased RFA was shown as a safe ablation technology. Andrade, et al., reported a safety profile in the meta-analysis with a complication rate of 2.0%, including an 0.63% incidence of thromboembolic complications (20). Recently a large survey (21) on RF ablation of AF has been published. It has evaluated 2,748 patients (620 with persistent AF) from 20 European centers using the Phased RFA system. The overall complication rate was 3.9%, with a stroke and TIA incidence of 1.1%.

Twelve comparative or randomized studies have been published comparing platinum electrode catheter PVAC versus alternative conventional RF ablation catheters. Briefly, all studies demonstrated equivalent safety outcomes. The novel catheter design of the PVAC GOLD array may improve safety by reducing embolic events as it prevents electrode 1-to-10 interaction and allows for enhanced tissue contact due to the 20° forward tilt. This registry will collect information about complication rates linked to the Phased RFA system or to the procedure itself.

Major procedure related complications include vascular complications secondary to venous access, cardiac tamponade, embolic stroke, esophageal injury, phrenic nerve injury, PV stenosis, and reentrant tachycardia arrhythmias arising from ablations, mainly left Afl.

Endpoint Definition: Procedure-related and/or device-related adverse events as determined by investigator.

Analysis Methods: The number of patients with reported device and procedure related events will be summarized as a binomial variable; number and percentage of patients with events. Additionally, a Kaplan-Meier estimations will be used to summary the timing of the occurrence of safety events through 12 months. Time from onset to resolution of events may also be presented.

Measurements: Adverse events to be documented starting from the index procedure until the 12 months FU.

4.4.3 Statistical methods for ancillary objectives.

Characterize the acute procedural success rate

Rational: A cornerstone of the ablation procedure is to block electrical conduction from the PVs. According to guidelines (22) both, exit and entrance block, are equally accepted as confirmation of PVI and used as indicator of acute success.

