The "Procedure" CRF will be used to collect data about the ablation procedure and discharge from the medical center. Information regarding anticoagulation therapy, procedure summary information, sedation and consumables, PVI confirmation, cardiovascular medication, date and status at hospital discharge is to be collected. Verification of study defined AEs will be done during the procedure and at the moment of hospital discharge.

If the attempt to conduct Phased RFA ("index" procedure) is not successful for clinical or technical reason, patients will stay enrolled into the registry. If Phased RFA is repeated ("repeated" procedure) or re-do due

to arrhythmia recurrence, the “procedure” CRF should be filled in. Information about all Phased RFA attempts will be used for the analysis. If patient has re-do procedures with some other technology than Phased RFA, Procedure CRF is not required; information about technology which was used for re-ablation to be collected in eCRF “General FU”.

During the Phased RFA, the investigator may require use of other commercially available devices for other ablations such as Afi/LAT or other AF triggers. The use of other devices will be at the investigator’s discretion and use will be documented on the eCRF.

Hospital discharge needs to be completed when the patient is discharged from the hospital, this data to be collected as a part of the procedure visit. Information about date of discharge, reportable adverse event since the procedure and recommended medication information is to be collected. Post-ablation drug regimen is determined at clinical discretion of the treating investigator.

General Follow up visits (in hospital)

The “General” FU CRF will be used to collect data during all standard visits at the site within the following 12 months after the index or study procedure. Data to be collected include: arrhythmia assessment, diagnostics, symptoms, hospitalizations, ablation information and medication. If “General FU” will take place due to system/procedure related AE, “Adverse Event” CRF should be filled in additionally to the “General” FU CRF.

If at any moment during FU, the patient withdraws PIC/PDRF or PI receives information about the patient’s death, the “Exit” CRF should be filled in addition to the “General FU” CRF. All data collected prior to the patient exit will be used for analysis, unless different is required by local laws and regulations.

12 months FU (in hospital or by phone)

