If the patient appears in the participating medical center within 12 - 14 months after the index procedure, the “in hospital 12 months FU” CRF should be completed. If an “in hospital” visit does not occur after 13 months post index procedure, the site should apply all efforts to conduct interview by phone and document it in “12 months phone FU” CRF. The phone FU interview does not replace a medical checkup for the patient and serves as data collection, only.

Data to be collected during 12 months FU includes arrhythmia assessment, diagnostics, symptoms, hospitalization and re-ablations occurred since last visit, medications, QoL questionnaire.

To ensure a unified approach and to minimize possible bias, all sites will be trained to use the standardized “patient questionnaire for phone FU” with questions regarding parameters of interest equivalent to eCRF variables. In Germany, the phone FUs can be performed by Institut für Herzinfarktforschung, GmbH.

If study personnel obtain information during the phone FU that patient will appear in the hospital before the end of FU window, it is under site consideration to complete „12 months phone FU” CRF or conduct a medical check -up and complete „in hospital 12 months FU”.

Study Exit

Prior to exiting a patient from the study, it is recommended to follow the patient until all ongoing reportable AEs are resolved or unresolved with no further actions planned. Upon exiting from the study, no further study data will be collected or study visits will occur for the patients. All data available through the time of the subject’s exit will be used for analysis.

Patients are urged to remain in the study until the end of individual follow up but may be exited from the study for any of the following situations:

- Patient lost to follow up
- Patient chooses to withdraw (e.g., consent withdrawal, relocation to another geographic location)
- Investigator deems withdrawal necessary (e.g., medically justified, , failure of subject to maintain adequate study compliance)
- If patient were enrolled with the intention to perform Phased RFA, but get ablation with another technology
- Death

If patient has enrolled into study and vascular access was obtained with the intention of completing the study Phased RFA, but the subject did not receive any ablation energy, or complete entire study

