procedure, sites will be asked to keep patients enrolled for 30 days to ensure potential procedure / device related AEs are assessed and collected. If there are no related.

All subject deaths must be reported by the investigator to Medtronic on an Exit Form as soon as possible after the investigator first learns of the death.

In the event of a patient's death, the investigator is responsible to assess at their own discretion whether or not the death is related to the procedure and/or the system.

If any relatedness is assessed, it is required also the completion and reporting of a Serious Adverse Event (SAE) form (see paragraph 11.1.1). Data collection requirements are summarized in Table 7-1 below.

Table 7-1: Data collection requirements at subject visits

| Data Collection* | Baseline | Procedure | General FU | 12 Months FU | 12 Months FU by phone |
|--------------------------------------|--------------------|------------------|-------------------|---------------------|------------------------------|
| Enrollment (PIC/PDRF) | X | | | | |
| Demographics | X | | | | |
| Medical History [#] | X | | | | |
| Concomitant disease | X | | | | |
| Diagnostics | X | | X | X | X |
| Symptoms | | | X | X | X |
| Medication list | X | | X | X | X |
| Administrative information | | X | X | X | X |
| Anticoagulation pre-intra-procedural | | X | | | |
| General procedure summary | | X | | | |
| Consumables | | X | | | |
| PVI confirmation | | X | | | |
| Hospital discharge | | X | | | |
| Quality of Life (AFEQT) | X | | | X | X |
| History of AF since last visit | | | X | X | X |
| Hospitalization | | | X | X | X |
| Reportable Adverse events** (AEs) | - Whenever occur - | | | | |
| Study Exit | - Whenever occur - | | | | |
| Study Deviation form *** | - Whenever occur - | | | | |

* prior to first patient enrollment every site needs to fill in a site questionnaire once #= Medical history includes questions about prior CVD, history of AF, main underlying disease, concomitant disease and history of AF.

** Data collecting requirement for Adverse Event eCRF described in chapter 11 "Adverse Event"

*** Data collecting requirement for Deviation eCRF described in chapter 7.4 "Study Deviations"

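### For an index procedure that is started but not completed, the CIP requires follow-up to 12-14 months in two places but asks for only 30 days in Study Exit, putting later safety data and repeat attempts at risk

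*Protocol*

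**What the plan says.** The CIP synopsis (Individual FU duration) starts follow-up at the index procedure and says it "lasts 12 (+ 2) months". If the index procedure is unsuccessful, "patients will continue their participation in the registry until the end of defined FU period". Its examples include a procedure ended early because of the patient's condition or a technical problem.

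CIP 3.4 says that after an index procedure that was performed without success, "patients will stay in the registry until the end of the FU period". CIP 7.2 (Procedure visit) says that if the attempt "is not successful for clinical or technical reason, patients will stay enrolled into the registry"; it gives no duration.

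CIP 7.2 (Study Exit) takes a patient with vascular access obtained for the study procedure, "but the subject did not receive any ablation energy, or complete entire study" procedure. For this patient, "sites will be asked to keep patients enrolled for 30 days to ensure potential procedure / device related AEs are assessed and collected". The next sentence opens a condition about there being no related events and stops, at least in the public copy. One of the listed exit reasons reads "If patient were enrolled with the intention to perform Phased RFA, but get ablation with another technology".

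On safety, CIP 4.4.2 says: "Adverse events to be documented starting from the index procedure until the 12 months FU".

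**The concern.** A procedure stopped early is both an unsuccessful procedure (synopsis, 3.4, Appendix 1) and an incomplete one (Study Exit). The same patient can be kept for 12-14 months under one rule and released at about day 30 under the other. Two sites acting in good faith could differ, and the patients affected are those in whom the procedure went badly.

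After exit, CIP 7.2 ends data collection. Late complications and second attempts would go unrecorded in this group, while the safety analysis is meant to run to 12 months.

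**Working it through.** The point rests on no sample-size or power figure, so there is no plan figure to reproduce. The check sets the rules side by side and follows a day-30 exit through the SAP.

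**1. Do the two groups overlap?** Study Exit covers two kinds of patient.
- *No energy delivered.* CIP 3.4 speaks of an index procedure that was performed, so this group can be read as having had none. It is also outside the SAP's Baseline Analysis Set (BAS, SAP 4.2), which needs more than zero PV applications. There is no firm conflict here.
- *Energy delivered, procedure not completed.* The synopsis and Appendix 1 place this patient among the unsuccessful procedures, and Study Exit places the same patient under the 30-day request. No definition separates the two.

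**2. Where does day 30 fall?** SAP 8.1.2 ends blanking at day 90, and SAP 8.1.1 evaluates at day 351.
- 90 − 30 = 60 days before the first countable recurrence.
- 351 − 30 = 321 days of the 12-month safety period unobserved, or 321/351 = 91%.

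**3. Effect on each analysis for a partly treated patient exited at day 30.**
- *Main objective.* SAP 8.1.1 calculates it from a successful first procedure, judged by PVI confirmation. An unsuccessful case is outside it however long the follow-up, so the effect is about 0.
- *Safety.* SAP 8.2.1 analyses all procedures with RF applications, whether successful or not, at 30 days and 12 months. BAS needs no 12-month form, so the patient stays in the denominator. A patient with no documented event in the period is counted as event-free. The proportion in SAP 8.2.2 then treats one month of observation as twelve. The Kaplan-Meier estimate is less exposed if these patients are censored at exit.
- *Repeated procedures.* CIP 7.2 intends to use every Phased RFA attempt, and SAP 8.2.1 analyses additional procedures. An attempt after exit is not captured.
- *Full Analysis Set (FAS).* SAP 4.3 requires a valid 12-month form, so the patient cannot enter. SAP Appendix C predefines a FAS subgroup with a non-successful first procedure, which loses exactly these patients. They would instead appear as lost to 12-month follow-up in the Appendix C and D tables.

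**4. How many patients?** The documents give no rate of incomplete procedures. The nearest figures are acute success of 98.2% (paroxysmal) and 96.3% (persistent) in CIP 4.4.3.
- 1000 × (1 − 0.982) = 18
- 1000 × (1 − 0.963) = 37

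These are failures of any kind, including completed procedures that left a vein unisolated, so they are probably high for incomplete ones. They do not count same-session switches to another technology. Each end also treats all 1000 patients as one AF type.

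**5. Illustrative size for safety.** Understatement of the 12-month proportion = f × r, where f is the share exited and r their event rate after day 30. The documents give no r. Assume it equals the full complication rates quoted in CIP 4.4.2, 2.0% to 3.9%.
- 0.018 × 0.020 = 0.04 percentage points
- 0.037 × 0.039 = 0.14 percentage points

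Incomplete procedures may carry a higher r, and repeat attempts would add to it.

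**6. Illustrative size for success, only if all enrolled patients were analysed (CIP 4.1) with 90-day blanking.** Overstatement = f × (S − s), with S = 74% (CIP 4.4.1) and an assumed success s in incomplete cases of 0% to 54.1%.
- Low: 0.018 × (0.74 − 0.541) = 0.4 percentage points
- High: 0.037 × (0.74 − 0) = 2.7 percentage points

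The SAP's main analysis does not use this population.

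**The case against.** The case against has several sound parts.

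- *The headline rate.* A reader might infer that early exit of failures inflates the 12-month success rate. The SAP does not support this: unsuccessful first procedures are outside the main objective, and the Extended Full Analysis Set excludes them too. The range in step 6 applies only to a population that the SAP does not use for the main result. This objection stands.
- *The number of places.* It is tempting to count three places that require 12-14 months. Only the synopsis and 3.4 do. The Procedure visit text is consistent with them but would also fit a shorter period.
- *Permission to exit.* The 30 days can be read as a minimum. Study Exit also urges patients to remain to the end of follow-up and recommends following open reportable events to resolution before exit. Exit at day 30 is implied, not written. This weakens the claim but does not remove it, since the unfinished sentence is where the rule should have been.
- *The other-technology exit reason.* One might read it as letting sites release any patient whose procedure was finished with another catheter. The natural reading is substitution before Phased RFA starts. SAP 4.2 words the exit reason that way, and mixed-device procedures are expected and analysed (CIP 4.4.3, SAP 8.3.1). What remains is a difference in wording between CIP and SAP.

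None of this removes the conflict for a procedure begun with energy and stopped early. The SAP's treatment of safety, FAS and the subgroup does not depend on the main-objective restriction.

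**Conclusion.** The concern holds in limited form. For a partly treated, incomplete index procedure, the CIP gives two follow-up durations, and the SAP does not choose between them. If sites act on the shorter one, the main estimate moves by about 0. Late safety events and repeat attempts are lost, and the predefined non-successful subgroup is depleted.

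The number affected is unknown. Eighteen to 37 per 1000 is a proxy from acute failures and should not be read as a floor. On the assumptions in step 5, the overall safety proportion would be understated by roughly 0.04 to 0.14 percentage points. The larger damage is within the subgroup itself, where the lost patients form a bigger share. All of this assumes that sites do exit such patients near day 30, which the text allows by implication only. The correction is worth making because it is cheap and the loss would be selective.

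**What to change.** Reconcile the Study Exit text with the synopsis and 3.4:

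- Limit the 30-day request to patients with vascular access who received no Phased RFA energy.
- State that any patient with at least one Phased RFA application stays enrolled to the 12-14 month contact, by visit or the existing phone form, including when the procedure was stopped early or finished with another technology.
- Complete the unfinished sentence.
- Align the other-technology exit reason with SAP 4.2, so that it covers only patients in whom Phased RFA was not started.

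The change should apply to patients still enrolled. It should not extend to calling patients who have already exited, because CIP 7.2 ends data collection at exit.

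The cost is a short CIP clarification with a site notice, and a 15-20 minute phone contact (CIP 3.4) for a small number of patients. Only the length of data collection changes; treatment does not.

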7.2.1 Frequency of Follow up

Data collection will be completed following standard of practice procedures at each participating site. Most of the sites have a standard of care for post AF ablation visits to invite patients for the medical checkup after the "blanking period" which is lasts around 3 month after the ablation procedure; some sites also see patients at 6 and 12 months after the Phased RFA.

To mitigate variations in clinical care practices for analysis, the visit windows below are proposed to aligning with typical care practices for this therapy. Data analyses will include follow up visits, regardless of when they occur.

Table 7-2: Follow Up Visit Windows

| Months | Window Starts (days post procedure) | Target (days post-procedure) | Window end (days post-procedure) |
|-----------|-------------------------------------|------------------------------|----------------------------------|
| 3 months | 85 | 90 | 100 |
| 6 months | 175 | 180 | 190 |
| 12 months | 351 | 365 | 425 |

Additional data collection activities may be completed using sub-studies under the GOLD AF Registry protocol. Sub-studies may be developed to satisfy local data needs and/or evaluate additional areas of scientific interest. Sub-studies must be reviewed and approved by Medtronic and will be documented and managed under separate cover.

